3.3.4 Medical History

Medical history will be coded to system organ class and preferred term using the medical dictionary for regulatory activities (MedDRA) version 24.0. Counts and percentages of subjects with medical history by system organ class and preferred term will be summarized by treatment and in total based on the Enrolled Population. A medical review of the coding reports will be performed prior to database lock.

Stroke details such as stroke mechanism and symptomatic intracranial occlusion locations will also be summarized.

Comorbidities (such as autoimmune disease, cancer, active infection, COVID-19, hypertension, Transient Ischemic Attack (TIA), Cardiovascular accident (CVA), intracranial hemorrhage, head or spine trauma within past 3 months), smoking status, and additional medical history such as concomitant diseases or past surgeries will be listed.

3.3.5 Concomitant Medications

Any medication or vaccine (including over the counter or prescription medicines) that the participant is receiving at the time of enrollment through the Day 90 visit will be recorded. There are no restricted medications in this study. Concomitant medications will be coded to anatomical

therapeutic chemical (ATC) class and preferred term using the world health organization (WHO) Drug Dictionary B3 Global, March 2021. A medical review of the coding reports will be performed prior to database lock.

For summary purposes, medications will be considered prior medications if they were started prior to the date of starting infusion of study drug and not administered during infusion and concomitant medications if they were taken before and were continuing after the date of starting infusion of study drug or initiated after the date of starting infusion of study drug.

If a medication has incomplete start or stop dates, dates will be imputed to determine whether a medication should be considered prior or concomitant. If a medication start date is incomplete, the first day of the month will be imputed for missing day and January will be imputed for missing month. If a medication stop date is incomplete, the last day of the month will be imputed for missing day and December will be imputed for missing month. Incomplete start and stop dates will be listed as collected without imputation.

Counts and percentages of subjects taking prior and concomitant medications by ATC class and preferred term will be summarized by treatment and in total based on the Safety Population.

In addition, counts and percentages of COVID-19 vaccination, medications taken during the time of infusion, medications taken for an Adverse Event (AE), and any medications that the participant is receiving at the time of enrollment up to Day 90, including the type of intravenous thrombolysis tPA/TNK will also be summarized by treatment and in total based on the Safety Population.

3.3.6 *Eligibility Criteria*

Unmet eligibility criteria (inclusion not met/exclusion criteria met), date and time of stroke symptom onset (or if not known, last known well), whether the stroke symptom(s) was witnessed, whether subject experienced stroke on awakening, dates and times of informed consent signed, how consent was obtained (use of LAR) and randomization (study drug assignment) will be listed for the ITT Population.

3.3.7 *Study Drug Exposure and Compliance*

Total time of exposure to study drug will be calculated as stop time of infusion minus start time of infusion in units of hours (to the closest tenth). Note that the exposure calculation is intended to describe the length of time a subject was exposed to study drug and therefore does not take study drug interruptions into account. Time of exposure to study drug will be summarized by treatment assignment and in total based on the Safety Population with descriptive statistics. Infusion interruption is defined as study drug infusion stopped > 60 minutes.

Percent compliance (per subject) to the study drug regimen will be calculated as:

$$100 \times \text{total time of infusion} / 48 \text{ hours.}$$

Total time of infusion (per subject) will be calculated as:

$$(\text{stop time of infusion} - \text{start time of infusion}) - (\text{restart time of infusion} - \text{suspend time of infusion}).$$

If the infusion is not interrupted, the stop time (restart time of infusion – suspend time of infusion) will be considered 0 for the compliance calculation. Percent compliance to the study drug regimen will be summarized by treatment and in total based on the Safety Population with

descriptive statistics and with counts and percentages of subjects with compliance in the following categories:

- <80%
- 80-120%
- >120%

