5.1 Inclusion Criteria

- 1) AIS selected for emergency endovascular treatment.
- 2) Age 18 years or older.
- 3) Stroke symptom onset or, if not known, last known well time to randomization within 24 hours.
- 4) Disabling stroke defined as a baseline NIHSS score:
 - a. NIHSS > 5 for internal carotid artery (ICA) and M1-middle cerebral artery (MCA) occlusion; or
 - b. NIHSS > 10 for M2-MCA occlusion.
- 5) Confirmed symptomatic intracranial occlusion at one or more of the following locations: Intracranial carotid I/T/L, M1 or M2 segment MCA. Tandem extracranial carotid and intracranial occlusions are permitted.
- 6) Pre-stroke (24 hours prior to stroke onset) historical modified Rankin Scale (mRS) ≤ 2 . Patient must be living independently without requiring nursing care.
- 7) Qualifying imaging performed less than 2 hours prior to randomization.
- 8) Consent process completed as per applicable laws and regulation and the IRB requirements.

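### SAP 3.3.5 leaves medications first given on the infusion start date, and some stopped on it, neither prior nor concomitant, so they drop out of the ATC/preferred-term tables

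*SAP*

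**What the plan says.** SAP 3.3.5 (Concomitant Medications) sets up two classes for summary purposes.

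- Prior: "medications will be considered prior medications if they were started prior to the date of starting infusion of study drug" "and not administered during infusion". Both conditions must hold.
- Concomitant, first branch: "if they were taken before and were continuing after the date of starting infusion of study drug".
- Concomitant, second branch: "or initiated after the date of starting infusion of study drug".

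The main tables rest on these classes: "Counts and percentages of subjects taking prior and concomitant medications by ATC class and preferred term will be summarized by treatment", in the Safety Population. Incomplete start and stop dates are imputed at the level of day and month.

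The last paragraph of the section adds further counts and percentages by treatment that do not depend on the classes. They include medications taken during the infusion, medications taken for an adverse event, and any medication received from enrollment up to Day 90, with the type of intravenous thrombolysis (tPA/TNK) named.

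Protocol 6.7 requires start and end dates for each medication and does not ask for a time of day. Protocol 9.3.2 says only that prior and concomitant medications will be summarized with the WHO Drug Dictionary. It contains no rule that would settle a start on the infusion date.

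**The concern.** The prior rule looks strictly before the infusion start date and the concomitant rules look strictly after it or across it. The date itself belongs to neither. In most trials this would be a trivial edge. Here the infusion must begin within 30 minutes of randomization and before arterial access closure (Protocol 5.5 and 6.2), so the infusion start date is normally the date of the thrombectomy, a day on which new acute medication can be expected.

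At stake is the completeness of the by-arm medication tables in the population used for safety. Protocol 2.3.1 gives fluid overload as the major possible risk, and SAP 3.5.3 compares maximum blood pressure deviation to Day 2 between arms. A reader of those results would look to the medication tables for same-day drugs acting on blood pressure or fluid balance, where such drugs were given. If the rule is programmed as written, those drugs are missing. If a programmer notices the gap, they are assigned by a choice that the SAP does not record.

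**Working it through.** There is no figure in the plan to reproduce. The check applies the stated rules to cases.

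**Inputs.** The prior rule and the two concomitant branches are from SAP 3.3.5. The 48-hour infusion is from both documents. Assumed for illustration: the infusion starts at 12:00 on its start date.

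**Rules on calendar dates.** Let D be the infusion start date.

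- Prior: start date < D, and not given during infusion.
- Concomitant: (start date < D and stop date > D), or start date > D.

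| Medication | Prior | Concomitant | Given during infusion |
|---|---|---|---|
| Given and finished the day before D | yes | no | no |
| Long-term, stopped on D before infusion | yes | no | no |
| Long-term, stopped on D after infusion start | **no** | **no** | yes |
| Long-term, continuing | no | yes | yes |
| On D, 10:00 to 11:00, finished before infusion | **no** | **no** | no |
| On D, 11:00 to 14:00, spanning infusion start | **no** | **no** | yes |
| On D, 15:00 to 16:00 | **no** | **no** | yes |
| Started on D at 20:00, continued to Day 90 | **no** | **no** | yes |
| Started the day after D | no | yes | yes |

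**Systematic check.** Take hourly start times from 72 h before to 96 h after midnight at the beginning of D, and every later hourly stop time up to 120 h.

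- Starts on D: for start hour s = 0 to 23 there are 120 − s stop times, so 24 × 120 − (0 + 1 + … + 23) = 2880 − 276 = 2604 combinations. All 2604 are in neither class.
- Of these, 12 + 11 + … + 1 = 78 end by 12:00, so the during-infusion summary would not pick them up either.
- Started before D, given during infusion, stopped on D: 72 start hours × 11 stop hours (13:00 to 23:00) = 792 combinations. All 792 are in neither class.

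Changing the second concomitant branch to on or after the date classifies the 2604 but leaves the 792. Defining concomitant as everything that is not prior leaves none, by construction.

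These counts show that the gap does not depend on stop time and that there are two gaps. They are counts of constructed combinations and say nothing about how often such drugs occur.

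**Could date mean date and time?** The surrounding text points the other way. SAP 3.3.6 lists dates and times where both are wanted, SAP 3.3.7 uses infusion start and stop times, the imputation in 3.3.5 works on days and months, and Protocol 6.7 requires dates.

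**The case against.** The strongest reply is that SAP 3.3.5 already reports most of what the two classes miss. Thrombolysis type is named for its own summary, drugs taken during the infusion are counted, and the enrollment-to-Day-90 summary is close to a catch-all. All are by treatment in the Safety Population. Data listings are to show all available data (SAP 6.5). That stands. On a strict reading, the drugs left out of every summary are narrow: a non-thrombolytic drug started on the infusion date and finished before enrollment, and not taken for an adverse event. What does not stand is that these summaries complete the main tables. They are not stated to be by ATC class and preferred term, and they leave the definitions as they are.

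A second reply is that SAP 6.5 defers detail to separate programming specifications, which may settle the tie. They may. But the SAP states a rule, and a specification that departed from it would need to say so.

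Several stronger readings are tempting, and the documents do not support them.

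- A reader might infer that about nine in ten patients have their acute drugs unclassified. The protocol requires "Qualifying imaging performed less than 2 hours prior to randomization" and infusion within 30 minutes of randomization, so imaging to infusion takes at most 2 + 0.5 = 2.5 h. If arrival times are uniform, which is an assumption, at most 2.5/24 = 10.4% of patients cross midnight in that interval. That bounds midnight crossings. It does not measure the share of drugs unclassified, and drugs started on any later date are concomitant.
- A reader might equate the infusion date with the stroke date. Randomization may be up to 24 hours after onset or last known well (Protocol 5.1), so a drug given and finished on the previous calendar date is classified as prior in the ordinary way.
- A reader might conclude that thrombolysis goes unreported, that anaesthetic drugs are lost, or that listing flags will be wrong. Thrombolysis has its own summary. The documents do not name anaesthetics as recorded medications. The classes are set for summaries only, and no listing flag is specified.

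**Conclusion.** The point holds as a defect in wording. Followed literally, SAP 3.3.5 leaves two kinds of medication outside both classes: those first given on the infusion start date, and those begun earlier, given during the infusion and stopped on that date. The prior and concomitant ATC/preferred-term tables by arm would be incomplete.

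The size is small. Only descriptive tables are touched. The primary safety endpoints (SAP 3.4.1) and the efficacy models (SAP 3.4.2) do not use these classes, and the possible post-hoc covariate for thrombolytic use (SAP 3.4.4.3) is not defined through them. The number of affected drugs cannot be estimated from the documents. The conclusion assumes that date means calendar date and that the unseen programming specifications contain no rule of their own for the tie.

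**What to change.** Replace the definitions in SAP 3.3.5 with two exhaustive classes based on dates.

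- Prior: started before the infusion start date, stopped on or before that date, and not given during the infusion.
- Concomitant: every other recorded medication, including any started on or after the infusion start date and any given during the infusion.

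This closes both gaps. The stop-date condition also stops a drug that was paused for the infusion and later resumed from counting in both classes, as the present wording allows. Where the record does not show whether a drug stopped on the infusion date was given during the infusion, the SAP should state a default; concomitant is the natural one.

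The cost is one SAP sentence and the matching derivation, with no new data. There is one small downside. A drug started and finished on the infusion date before the infusion began is labelled concomitant unless a recorded time shows otherwise. A rule based fully on clock times would avoid that, but it would rely on times that the protocol does not require. The separate tPA/TNK summary still identifies thrombolysis.

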3.4 Safety and Efficacy Assessments

The primary safety analysis will be conducted in the Safety Population. The secondary efficacy analysis will be conducted in the ITT and PP Populations.

3.4.1 *Primary Safety Endpoints*

Frequencies and severities of SAEs

The proportion of participants with SAEs through Day 90 between the three treatment groups (RNS60 0.5 mL/kg/h, RNS60 1.0 mL/kg/h, and placebo 1.0 mL/kg/h)

In addition, the frequency and severity categories will be summarized with counts and percentages of SAEs by treatment and site and in total. See Appendix C for definition of SAE.

90-day Mortality

The proportion of participants alive at Day 90 between the three treatment groups (RNS60 0.5 mL/kg/h, RNS60 1.0 mL/kg/h, and placebo 1.0 mL/kg/h).

3.4.2 *Secondary Efficacy Endpoints*

All outcomes will be assessed in the following hierarchical order (to control of the overall Type I error rate). As it is hypothesized that higher dosage will result in less disability, subjects receiving placebo 1.0 mL/kg/h will first be compared to RNS60 1.0 mL/kg/h and then, as a lower ranking secondary endpoint, combined RNS60 doses (1.0 mL/kg/h and 0.5 mL/kg/h) compared to placebo, and finally RNS60 0.5 mL/kg/h compared to placebo. Specifically, efficacy of each of the 5 key endpoints will be assessed between high-dose RNS60 compared to placebo, followed by the same endpoints between combined RNS60 doses (1.0 mL/kg/h and 0.5 mL/kg/h) compared to placebo, finally followed by the same 5 endpoints between RNS60 low dose (0.5 mL/kg/h) compared to placebo:

1. Disability based on mRS score, high-dose vs placebo
2. Infarct progression/regression, high-dose vs placebo
3. NIHSS score, high-dose vs placebo
4. Worsening of stroke high-dose vs placebo
5. BI, high-dose vs placebo
6. Disability based on mRS score, combined-dose vs placebo
7. Infarct progression/regression, combined-dose vs placebo
8. NIHSS score, combined-dose vs placebo
9. Worsening of stroke, combined-dose vs placebo

10. BI, combined-dose vs placebo
11. Disability based on mRS score, low-dose vs placebo
12. Infarct progression/regression, low-dose vs placebo.
13. NIHSS score, low-dose vs placebo
14. Worsening of stroke, low-dose vs placebo
15. BI, low-dose vs placebo

If a comparison listed above is determined to be not statistically significant, then the remaining comparisons in the hierarchy will be tested in any case and interpreted in an exploratory manner.

In addition to the primary time point of each endpoint (as defined below), all other applicable time points will be compared as well and interpreted in an exploratory manner.

In these analyses, testing the combined-dose versus placebo will be done within the statistical models by averaging the results in the two active doses and comparing to placebo. (This is in contrast to performing a separate analysis in which subjects on active dose are treated as a single treatment arm.)

Generalized linear mixed models will be implemented for the analyses of disability based on mRS, infarct volume, NIHSS at 24 hours, worsening of stroke, and Barthel Index. NIHSS will be analyzed on the recorded scale of measurements and the treatment groups' Least Squares (LS) means, corresponding 95% confidence intervals (CIs), and LS mean differences will be reported. Disability based on mRS, worsening of stroke, and Barthel Index are dichotomized endpoints that will be analyzed on the logit scale of measurement. The resulting LS means and confidence intervals will be back-transformed to probabilities, and differences in least squares means will be reported as odds ratios. Infarct volume will be analyzed as log-normally distributed, and descriptive statistics will be geometric means where between-group comparisons will be reported as ratios of geometric means. Covariates baseline NIHSS and ASPECTS binary factors for efficacy analysis will use baseline values from the Electronic Data Caputre.

1. Modified Rankin Scale (mRS) score:

The effect of treatment on global disability at Day 90 will be examined by comparing the proportion of subjects who had disability (Yes or No) between the three treatments (RNS60 1.0 mL/kg/h, RNS60 0.5 mL/kg/h, and placebo 1.0 mL/kg/h) using generalized linear mixed modeling (GLM) using residual pseudo-likelihood with a subject-specific expansion(RSPL) assuming a binary outcome (0-2=0, 3-6=1). Covariates include the Age, baseline NIHSS, and ASPECTS binary factors used for block urn randomization and baseline (pre-morbid) mRS, baseline occlusion location, study site, baseline perfusion status, and log of baseline infarct volume. Treatment, visit day, and interaction of treatment and visit day are included as categorical fixed effects.

An unstructured covariance structure will be applied for GLM. In case the model will not converge with the unstructured covariance structure, Heterogeneous Autoregressive (1) (ARH(1)), Heterogeneous Compound Symmetry (CSH), Autoregressive(1) (AR(1)) or Compound Symmetry (CS) covariance structure will be used instead in this order until convergence is achieved.

The predicted probability for each treatment group and least squares (LS) mean difference between high-dose and placebo and low-dose and placebo groups along with the 95% confidence intervals (CIs) for Day 90 will be provided using the LSMEANS/DIFF statement with the ILINK option. The comparison of the two combined active arms versus placebo will be performed using the LSMESTIMATE statement. The odds ratio will also be calculated. The P-value for the hypothesis testing will also be provided. Treatment difference will be assessed with a 2-sided alpha level of 0.05, verifying, however that any statistically significant finding is consistent with the alternative hypothesis of efficacy versus placebo.

The sample SAS code planned for the analysis is outlined below.

Summary of dichotomized mRS endpoint (0-2 indicating a value of 0 and 3-6 indicating a value of 1) with counts and percentages of subjects will be generated to compare baseline mRS with Day 90 for each treatment arm and for the two active arms combined.

Horizontal bar graphs will be generated to visualize mRS distribution at Day 90 across all treatment groups. mRS score at Day 90 will be displayed where bars will be labelled with subject counts and proportions.

KEY SENSITIVITY ANALYSIS (analysis assuming Missing Not At Random (MNAR))

The analysis consists of the following steps:

1. Imputation of all intermittent missing data with multiple imputation (MI) assuming MAR, in order to generate a dataset with monotone missing data structure. The endpoint being modeled will be the mRS on the original 0-6 scale, rather than the derived binary endpoint.
2. Based on dataset generated in Step 1: imputation of all monotone missing data with MI assuming MAR, in order to generate dataset with no missing data
3. Based on dataset generated in Step 2 (with no missing data): all visits that have monotone missing data that are not due to COVID-19 will be set back as missing for subjects in the active arm.
4. Based on dataset generated in Step 3: imputation of remaining monotone missing data (not related to COVID-19) with multiple imputation assuming MNAR (Copy-Reference imputation).
5. Based on data generated in step 4, analysis of imputed data with GLMs
6. Combination of results from GLMs.

Step 1: Imputation of intermittent missing data

Based on dataset generated in Step 1, a seed value of 2001 will be used. The imputation is based on the MAR assumption, i.e. the missing data are assumed to follow the same model as for the other subjects in their respective treatment arm. Age, baseline NIHSS, and baseline ASPECTS are included as a factor in the model because the randomization is stratified by these factors.

The following SAS code will be used to generate the monotone missing data pattern:

A series of horizontal black bars of varying lengths, representing redacted SAS code. The bars are positioned vertically, with some longer ones at the top and bottom and shorter ones in the middle.

If any of the treatment levels has no missing data, the data from the treatment level in question will be excluded from the PROC MI procedure above (using WHERE statement). If this is done, the observed data from the treatment level in question (without any missing data) will be added to the output dataset produced above 500 times, i.e. once for each round of imputation.

Step 2: Imputation of missing data with assumption of MAR

Using the dataset generated in Step 1, all remaining missing values will be imputed based on the assumption of MAR. The following SAS code will be used for the imputation assuming MAR.

A series of horizontal black bars of varying lengths, representing redacted SAS code. The bars are positioned vertically, with some longer ones at the top and bottom and shorter ones in the middle.

Step 3: Setting monotone missing data that are not due to COVID-19 back as missing

After Step 2, information on reason for missing data (by subject and visit) will be merged to the dataset that contains no missing data. Within each subject, data from the visits that have monotone missing data that are not due to COVID-19 will be set back as missing for subjects in the active arms.

Step 4: Imputation of remaining missing data (non COVID-19 related) with assumption of MNAR

The dataset generated in Step 3 (which contains monotone missing data) will be imputed based on the assumption of MNAR, using Copy-Reference imputation. The MNAR imputation will be based on trajectories in the placebo group, i.e., data from the placebo group only will be used to generate the imputations. This step will include data for active subjects identified in step 3 along with all placebo subjects. For this, the MNAR statement will be used as described below.

Step 5: Analysis of imputed data with GLM

The imputed datasets generated in Step 4 do contain only non-missing values and are used as input in the statistical model. The final step before statistical inference is to convert the imputed mRS data (on the 0-6) scale to the binary endpoint (0-2, 3-6). Residual pseudo-likelihood with a subject-specific expansion (RSPL) based GLMs will be run on each of the 500 generated imputed datasets. For additional details on how to specify the GLM, see the analysis section corresponding with this sensitivity analysis.

Step 6: Combination of results from the GLMs

Finally, the MIANALYZE procedure in SAS will be applied to combine the 500 results from the analyses generated in Step 4, to derive an estimate of the treatment difference at day 90. In addition to the estimate, corresponding two-sided 95% CIs and p-values will be generated with the MIANALYZE procedure.

2. Volume of stroke or Infarct volume (Diffusion-weighted imaging, DWI):

Infarct progression/regression will be analyzed as measured by MRI brain imaging. Where MRI was not available, infarct volumes will be obtained from a 48-hour CT imaging. Infarct volume will

be summarized with descriptive statistics at Baseline, 24 hour, 48 hour, and Day 90 timepoints. The volume difference between 48 hour and 24 hour and between Day 90 and 24 hour timepoint will also be summarized.

The simple effect of treatment on Infarct progression/regression will be examined by 48-hour infarct volume on a log scale between the three treatments (RNS60 1.0 mL/kg/h, RNS60 0.5 mL/kg/h, and placebo 1.0 mL/kg/h) using GLM using maximum likelihood assuming a Gaussian distribution. Covariates include the log of baseline infarct volume along with Age, baseline NIHSS, ASPECTS binary factors used for block urn randomization, baseline perfusion status, baseline occlusion location, and study site.

